3.0 Objectives

The use of polypharmacy in Veterans, especially for the treatment of PTSD and traumatic brain injury, has increased over the past two decades, exposing Veterans to risks for drug-drug interactions and adverse side effects. Use of a pharmacogenetic tool that could give providers essential information needed to optimize Veteran's medication regimen has the potential to improve Veteran health outcomes, reduce risks for adverse events, and reduce treatment utilization costs.

This project is designed to evaluate the effectiveness of pharmacogenetic testing in individuals who are prescribed psychiatric polypharmacy. The study will test the following hypotheses:

- Use of pharmacogenetic testing and the G-DIG will reduce psychiatric polypharmacy.
- Use of pharmacogenetic testing and the G-DIG information provided to providers will result in changes to the medication treatment plan based on the new information.
- Use of pharmacogenetic testing and the G-DIG will improve overall clinical symptoms as measured by the CGI (secondary analyses).
- Pharmacogenetic testing and the G-DIG will reduce healthcare costs associated with medications (secondary analyses).
- Pharmacogenetic testing will reduce clinical symptoms of anxiety and depression and improve quality of life (secondary analyses).

5.0 Study Procedures

5.1 Study Design

This is a 12-week open-label, naturalistic study of the provision of pharmacogenetic testing information to both providers and patients. Veterans who have been prescribed polypharmacy and are experiencing a sub-optimal effect will be eligible for the study. Medication providers who are participating in the study as sub-investigators will refer their own patients for the study. Eligible patients will be given the opportunity to participate in this study. Informed consent will be obtained by research staff who are not the potential participant's provider to avoid any undue pressure to participate.

If the potential participant signs consent, a cheek swab sample will be obtained in order to complete the pharmacogenomic testing. The genetic information will be sent to Genomind for processing using only a unique study number. No personal health information will be shared with the sponsor. Participants will be asked to complete a short battery of psychological measures, including measures of depression, anxiety, PTSD, insomnia, pain, drug and alcohol use, quality of life, side effects, and medication adherence (See Appendix A).

After the participant signs the consent form, they will enter a 2-week baseline period. During these 2 weeks, the pharmacogenetic test results will be available online for providers. Prior to receiving the results, providers will draft an initial medication optimization plan without the benefit of the pharmacogenetic information. The provider will also complete a Clinical Global Impression-Severity (CGI-S) rating of overall severity of symptoms for their client, and will document the participant's primary and secondary (if any) diagnoses.

When the results of the pharmacogenetic testing are ready, providers will review results using a secure web-based program and will utilize the G-DIG tool in order to determine the optimal medication regime for the patient, based on their individual genetic profile. Genomind will provide training to all investigators prior to the study start regarding the interpretation of the pharmacological assay and the use of the G-DIG tool. Genomind representatives will be available throughout the duration of the study for consultation regarding the interpretation and implementation of the testing results. For each provider, consultation is mandatory for the first two subjects and then available as needed for further subjects. If the patient is on a medication that is not currently listed in the G-DIG, the provider will inform the sponsor, and that medication will be added to the G-DIG tool. All final decisions about changing dosage, adding medications, or removing medications will be determined by the provider.

The provider will design an optimized, individualized medication regimen for the participant and document this revised plan. All clinical decisions regarding medical treatment and making any changes to medications will be made by the treating provider and their patient. Any medications that might be recommended by the testing results but are not provided by the VA's pharmacy (not on formulary) will be noted. Providers will then contact their patients by phone, mail, and/or schedule an in-clinic appointment for the subject (this can be scheduled at the initial consent appointment) to review the pharmacogenetic assay results and implement the medication optimization plan. Any medication changes will be dispensed by the pharmacy either in person or can be sent to the participant by mail. The provider will have 2 weeks (± 2 weeks) to review these results and contact the patient.

After the 2-week baseline, future appointments between the provider and the participants will be conducted consistent with treatment as usual. It is recommended that appointments around 6 and 12 weeks (within a three week buffer) be scheduled, but this is up to the discretion of the provider and the needs of the patient. The provider will complete a CGI-Improvement (CGI-I) measure at appointments within the 6 and 12 week windows, as available.

Study staff will contact the participant at 6 and 12 weeks by phone to conduct phone interviews to repeat the measures of depression, anxiety, PTSD, insomnia, pain, drug and alcohol use, quality of life, side effects, and adherence. Study staff will also complete a CGI-I assessment. Study staff collecting the participant ratings will be blind to any medication changes made until the end of the subject's participation in the study. After the 12 week assessment, study staff will review the medical record to determine changes in medications.

During the consenting process, subjects will be presented with an additional consent in order to allow researchers to add the data into a research repository. Subjects can choose whether or not to participate. If they do, their data will be entered into the repository. If they do not, their data will be kept during the time of the study and maintained as per IRB rules and regulations.

Risk/Benefit Ratio: This study naturalistic study presents only a limited risk to subjects and is associated with the possible benefits of reducing polypharmacy, improving symptoms, and reducing the risk of adverse events. Essentially, the only intervention in this study is the provision of additional data to the provider that may aid in choosing more appropriate medications.

Potential risks of this study include participants becoming uncomfortable with questions asked on the survey, potential for breach of confidentiality, and the risk that if the assay provides poor advice, a medication chosen may not have the desired effect (of course this is always a risk when prescribing any medication and is not exclusive to this study). Since this is a naturalistic study,

side effects of medication treatment are an expected part of treatment as usual and will be handled by their provider as part of their regular clinical care.

Vulnerable Populations: This is a naturalistic study, so we are interested in opening it up to a representative sample of Veterans in order to evaluate the potential benefit of receiving the pharmacogenetic test results. Since all subjects would already have been prescribed polypharmacy, providing their medication providers with information about how their body processes medications may be helpful to reducing the number of medications and potentially improving symptoms and reducing side effects. This study does not recommend the prescribing on any medication. All decisions regarding medication prescriptions will be made by the provider and the participant. Thus, vulnerable populations are at no greater risk for participating in the study, and participation may actually reduce risks of polypharmacy and the potential for adverse effects. In order to conduct this naturalistic study is it essential to enroll persons with mental health diagnoses. However, those patients who in the clinical judgment of their provider have impaired decision making capacity that may affect their ability to provide informed consent will not be enrolled into the study. In addition, those who have a guardian for health care decisions will not be enrolled in the study. Another vulnerable population is pregnant women. Requiring a pregnancy test to exclude women who are pregnant would represent an invasion of privacy since this study does not represent any known increase risk to an unborn fetus. However, as per IRB request, if a woman self-identifies as being pregnant, she will be excluded from the study.

Study Map:

Procedure	Initial Consent Appointment	Baseline Period of 2 weeks	Week 6	Week 12
Consent	X			
Pharmacogenetic testing	X			
Provider documents initial medication plan	X			
Provider reviews pharmacogenetic testing and uses G-DIG tool		X		
Provider develops optimized medication plan		X		
Provider contact patient & contacts pharmacy to make medication changes as needed		X		

Patient measures	X		X	X
CGI	X		X	X
Demographics	X			
PHQ-9	X		X	X
GAD-7	X		X	X
PCL-5	X		X	X
VR-12	X		X	X
PEG	X		X	X
PSEQ	X		X	X
ISI	X		X	X
Drug & Alcohol Screening	X		X	X
Side Effects	X		X	X
Medication Adherence	X		X	X

Pharmacogenetic Sample: Genomind will provide the Genecept Assay® Test Kits for this study. The kits contain all of the specimen collection and shipping materials (e.g. buccal swab, FedEx shipping materials and prepaid shipping label). The biological sample will be collected by cheek swab. The de-identified sample will be sent FedEx. The sample will only be identified with a unique assay ID number, that is separate from the study ID number. All samples will be processed by Genomind and the results will be added into the G-DIG tool, which can be accessed by the provider through the Genomind Clinician Portal, a secure website maintained by Genomind. Because the assay results may provide important information that would be relevant and pertinent to more than just the psychiatric medication provider, subjects will be given the opportunity to sign a separate release of information to allow researchers to share the Genecept assay results with the subject's other medical providers who may benefit from the assay information. Providers may also provide the subject with a paper copy of the test results if clinically appropriate. The assay will be identified by the unique assay ID number, which will be separate from the study ID number. The biological sample itself will be destroyed within 90 days by Genomind. Documentation of destruction of the biological sample will be provided by Genomind at the end of the study.

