5.4 Inclusion/Exclusion Criteria

Inclusion Criteria

1. Currently receiving outpatient treatment for a mental health diagnosis within the VA Puget Sound Health Care System from a provider who is a sub-investigator on this study.
2. Currently experiencing a sub-optimal medication response as assessed by either continued symptoms or medication side effects, which in the opinion of their treating provider would indicate a change in medications would be warranted.
3. Currently prescribed polypharmacy, as defined as five or more medications, with at least two being for a mental health diagnosis. Also allowable would be one medication for a mental health diagnosis and another medication for side effects related to a medication prescribed for the mental health diagnosis.
4. Between the ages of 18 and 75.

Exclusion Criteria

1. Any mental or physical health diagnosis, which in the opinion of their treating prescriber would prevent them from being compliant on a medication regimen or being able to complete the study measures.
2. Current/active diagnosis of severe alcohol or drug use disorder.
3. Serious medical or mental health symptoms requiring immediate stabilization and/or hospitalization.
4. Impaired decision making capacity that in the clinical judgement of their provider would affect their ability to provide informed consent.
5. Self-identification as being currently pregnant.

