Insomnia Severity Index (ISI) – The ISI (Bastien et al., 2001) is a brief screening of insomnia and is designed to be used as a research outcome measure. The scale is based on the DSM-IV criteria for insomnia and measures the individual's difficulty with falling asleep, staying asleep, or waking early in the past two weeks. Additional questions ask about sleep satisfaction and the impact of their sleep problems on their quality of life.

Drug and Alcohol Screening: These brief screening tools for drug and alcohol use include questions regarding the use of alcohol in the past year and the use of drugs of abuse in their lifetime and then how often they used any drug mentioned in the past three months. This measure is included as part of the BHL (Oslin et al., 2006).

Demographic Questionnaire: A standard measure of demographic will obtain information regarding age, gender, race/ethnicity, level of education, current housing, current employment, and military service. This questionnaire also queries about smoking. These questions will be asked only once at baseline. This measure is included as part of the BHL (Oslin et al., 2006).

Side Effects and Medication Adherence: participants will be queried on their actual adherence to the medications prescribed, actual dose taken, and doses skipped, will be queried. They will also be asked about common side effects and be given an opportunity to report any other side effect that they are experiencing. This measure is included as part of the BHL (Oslin et al., 2006).

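### The staff CGI-I is described as blind to medication changes, but the same calls ask about side effects, adherence and doses taken, so the blind is not secured and should be called partial

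*Combined protocol and SAP*

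**What the plan says.** Section 5.1 sets out the blind: "Study staff collecting the participant ratings will be blind to any medication changes made until the end" of the subject's participation. It backs this with one safeguard: "After the 12 week assessment, study staff will review the medical record to determine changes in medications".

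The same section has staff telephone participants at weeks 6 and 12 to repeat the baseline battery. The list of measures ends, and the rating follows, in these words: "side effects, and adherence. Study staff will also complete a CGI-I assessment". Section 5.5 gives the staff CGI rating to the study coordinator or to whoever collects the assessment measures. The provider also rates the CGI.

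Appendix A (section 11.0) describes the side-effect and adherence measure: "participants will be queried on their actual adherence to the medications prescribed, actual dose taken, and doses skipped". Participants are also asked about common side effects and can add any others. The measure is given at the consent visit too ("quality of life, side effects, and medication adherence (See Appendix A"), and the study map in section 5.1 marks it at all three time points: "Medication Adherence X X X".

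**The concern.** A rater who is to be blind to medication changes is asked, on the same call, to question the participant about medications and doses. The study is open-label, so the participant has no reason to withhold a change and is not told to. Deferring the chart review does nothing about what the participant says.

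What is at stake is how far the staff CGI-I can be relied on as a blinded rating. Section 5.5 makes the CGI the main measure of clinical effectiveness. The provider's CGI-I comes from the person who decides on the medication changes, so the staff rating is the only CGI rating for which blinding is claimed. A report that repeated the protocol's description would claim more than the plan secures.

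**Working it through.** **The plan's own figure.** The only design calculation is in section 5.6: about N = 34 for a single-sample t-test with effect size d = 0.50, alpha .05 and power 0.80. The sidedness is not stated. Taking it as two-sided, n solves P(|T| > t(0.975, n − 1)) = 0.80, where T is noncentral t with n − 1 degrees of freedom and noncentrality 0.50·√n. This gives n = 33.37, rounded up to 34. Power is 0.808 at N = 34 and 0.934 at N = 50. The figure reproduces. Rater blinding does not enter it, so the rest is a comparison of the text.

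**Comparison of the sections.**

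| Question | Where | What it settles |
|---|---|---|
| Who makes the staff CGI rating? | 5.5 | The coordinator or the person collecting the measures; no separate rater is required |
| What else is on that call? | 5.1 text and study map | Side effects and adherence, at both week 6 and week 12 |
| What do those questions touch? | Appendix A | Prescribed medications, dose actually taken, doses skipped, side effects |
| Does the respondent know of a change? | 5.1 | Yes; the design is open-label and providers go over the results with patients |
| Are there earlier answers to compare with? | 5.1, 5.5 | Yes; the same measure is given at baseline |
| What protects the blind? | 5.1 | Chart review waits until after week 12 |
| Is the order of the call fixed? | 5.1 | No. The text names the CGI-I after side effects and adherence; the study map lists the CGI above the PHQ-9 and puts those two measures last. Neither is an instruction |
| Is the blind checked? | Nowhere | No record of whether the rater learned of a change |

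**What follows.** The call opens a route by which the rater can learn of a change before scoring the CGI-I, and nothing in the plan closes it. Knowing earlier answers makes the inference easier, but the documents do not say that one person makes all of a participant's calls.

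**What is affected.** The number of medications comes from chart review, and changes to the treatment plan come from the provider's documented plans, so the first two hypotheses in section 3.0 are untouched. The staff CGI-I bears on the third, which is labelled secondary.

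**What reordering would do.** If the CGI-I is locked first at week 6, that call's answers cannot reach it; through this measure the rater can have heard only baseline answers, which were collected before the test results were available. At week 12 a rater who knows the week-6 answers may still know of a change. Reordering therefore narrows the route without closing it, which is why a record of rater knowledge is also needed.

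**The case against.** The strongest reply is that little depends on this blind. The study has one arm, every participant is tested, and section 5.6 plans a within-group test, not a comparison of changed with unchanged regimens. Raters already expect changes, because inclusion criterion 2 in section 5.4 requires a sub-optimal response "which in the opinion of their treating provider would indicate a change in medications would be warranted". Section 5.6 already asks for reservations about attribution. All of this stands and keeps the point small. It does not make the blinding statement accurate, and the section 5.6 caution concerns the missing control group, not what the rater knows.

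A second reply is that a global improvement rating should take side effects into account, since some patients enter because of them. That is a real trade-off. However, Appendix A describes the CGI as a measure of psychiatric function and improvement, and the symptom measures would still come first.

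Three stronger readings are tempting and are not supported:

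- *Every staff rating is compromised.* A reader might multiply 2 calls by 50 participants and call all 100 ratings unblinded. That counts calls on which the questions are asked, not calls on which a change is revealed. The actual items are not in the documents; Appendix A does not say that drug names or a medication list are taken down. The answers can reveal a change, and no percentage can be given.
- *Changes are in place by the week-6 call.* Section 5.1 says: "The provider will have 2 weeks (± 2 weeks) to review these results and contact the patient". That dates the contact, not the start of a change, and any new supply may be sent by mail. Some week-6 calls could come before any change.
- *The plan puts the CGI-I after the revealing questions.* The text and the study map point in opposite directions, so the order is simply not set.

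**Conclusion.** The blind stated in section 5.1 is not secured by the procedures in the same section and should be treated as partial. This is a minor point. It concerns the staff CGI-I and, through it, one secondary hypothesis; the medication-count and plan-change outcomes are unaffected. Neither the size nor the direction of any bias can be derived from the documents, and none is assumed here.

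The conclusion rests on two readings: that the person who collects the measures may also rate the CGI, which section 5.5 allows, and that the adherence questions follow their description in Appendix A. It does not require that the same person makes every call, although the route is wider where that is so. A reader should not conclude that the blind is known to be broken or that the CGI-I result is invalid; the documents show only that the blind can fail and that no one would know if it did.

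**What to change.** Make three changes in section 5.1.

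1. On each call, score and lock the staff CGI-I after the symptom measures and before the side-effect and adherence questions. Treat the severity item the same way if staff rate it at follow-up, as Appendix A implies. Leave the measures and their schedule as they are.
2. Add one yes/no item, completed when the CGI-I is locked: did the rater know of a medication change, including from an earlier call? Report the number of yes answers at weeks 6 and 12.
3. Replace the blinding statement with wording such as: *Study staff do not review the medical record for medication changes until after the week-12 assessment. They may learn of changes from participants, so the blind is partial.* Report the staff CGI-I in those terms.

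The cost is a reordered call, one extra item and a less favourable description of the blind. No staff, visits or patients are added. The staff CGI-I would be rated without that call's side-effect answers, which may make it slightly less comparable with the provider's CGI-I, for which no such order is set. If calls have already been made, the third change can still be applied in reporting.

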5.2 Recruitment Methods

Mental health patients within the VA Puget Sound Health Care System who have been prescribed polypharmacy will be eligible for this study. All providers participating in the study will be sub-investigators on this trial and will refer their own patients. Informed consent will be obtained by study staff other than the patient's own provider to reduce any undue pressure on the patient to participate. Patients will be fifty Veterans treated for a mental health diagnosis by an enrolled provider, who are prescribed polypharmacy

as defined as five or more active medications, with at least two for the treatment of a mental health disorder.

Subjects will be identified and recruited by their medication provider who is participating in this study as a sub-investigator. Study staff may assist study providers in identifying potential subjects by pre-screening upcoming appointments. When a potential subject has been identified, the study provider will introduce the study to the subject at their next clinical visit and ask if they would be interested in getting more information about the study, providing them with an informational flier. If the subject is interested, a study staff member would speak to the potential subject in a private area, review the consent form, and provide an opportunity for the subject to sign consent to participate in the study.

The subject will be paid by check the amount of \$20 per study visit, for a total of \$60 if they complete all the visits. It is expected that the measures will take less than an hour to complete, so this payment seems appropriate for the amount of time requested of the participant. Checks will be mailed from the VA R&D to the subject's home.

